7.2.6 Study Visit 5 – 12 week (4 weeks post treatment)

The subject will return in 4 week. The study visit will be 3 days before or 3 days after this time to account for weekends. At this final study visit, we will collect final routine bloodwork (1) LFTs (2) inflammatory markers in addition to another urine toxicology and urine pregnancy test. This is be approximately 5-10cc of blood or 1-2 teaspoons. We will complete final surveys 1) EHP-30 (2) PGA (3) PGIC (4) C-SSRS (5) FSFI (if partnered and sexually active). Physical assessment will be performed as outlined in 7.2.3.

If the subject has any abnormal test results or adverse events, these will be followed until their resolution at time intervals deemed appropriate by the clinical team. If there is an unforeseen pregnancy, the pregnancy will be followed throughout for adverse maternal, fetal and neonatal outcomes.

7.2.7 (Optional) Study Visit 6 (Eligibility window: 12-24 weeks post-enrollment)

At the initial enrollment visit, all subjects will be offered participation in the optional pharmacokinetic testing. If interested, they will complete consent during the main consent process and we will recruit until we have enrolled four participants and they have completed this Visit. As we are recruiting from the study participants, who will have already undergone rigorous screening throughout the initial study, we will not be repeating any additional testing on these patient. During this part of the study, they will also only be receiving a one-time dose of CBD. They will remain eligible to participate in this study for up to 3 months from the date of their last visit.

After completion of the initial study, the participants will undergo a 4 week washout period of the study drug, which will correspond with Visit 5 (4 week post-treatment visit).

At this time, screening measures have been set forth by the institution to test for SARS-CoV2 (the virus that causes COVID-19) if a study participant is planning to stay overnight at the Clinical Research Center.

The subjects will be screened via telephone prior to testing.

- If negative, they will proceed to testing.
- If positive, they can be rescreened in 1 or more weeks. If negative, they can proceed to testing. This can continue until the participant is no longer eligible for this portion of the study.

COVID-19 testing is currently required 5 days prior to study participation to allow appropriate time for the test to result. Testing will be done via PCR using a nasopharyngeal swab that will be

sent out to Quest Diagnostics. Once they have obtained COVID-19 testing, they will be asked to self-quarantine until their second visit at the CRC.

- If negative, they will be directed as per the COVID-19 Script for study participants when they arrive on site.
- If positive, their visit will be postponed and we will follow the COVID-19 Duration of Special Pathogen Isolation Precautions for Patients Diagnosed or Strongly Suspected to Have COVID-19 SOP for duration of isolation precautions. If they meet criteria for discontinuing isolation precautions, they will be allowed to participate in the study. Per the current SOP guidelines, positive COVID-19 patients should not be retested as according to the most recent data, there have no documented cases of re-infection worldwide.

We will continue to reference Penn State Health Pre-Operative and Pre-procedure COVID-19 Testing Standard Operating Procedure (SOP) for updated guidelines and will adjust our policies to most reflect the current institutional standards. If institutional policies change to no longer require COVID-19 testing, they will not be required for this study.

Subjects will then report to the Clinical Research Center (CRC) where they will plan to remain for 24 hours. A licensed professional will place an IV and the subject will undergo sequential blood draws to determine CBD pharmacokinetic parameters after administration of 20mg of sublingual CBD. Prior to initial administration of the CBD, a salivary pH will be obtained and recorded. They will be monitored overnight. They will then return to the CRC at 48 hours from the initial administration for one final blood draw. CBD levels will be measured using an internal assay developed at Hershey Medical Center. Approximately 10 teaspoons (about 50 ml) of blood will be drawn for this optional study visit. See details below.

Pharmacokinetic procedures: Blood will be drawn at time 0 hours, 0.25 hours, 0.5 hours, 1 hour, 2 hours, 4 hours, 8 hours, 12 hours, 24 hours and 48 hours following administration of 20 mg of sublingual cannabidiol. These time points are chosen to allow determination of the Cmax, and terminal half-life of CBD.¹⁹ Sublingual dosing affords higher bioavailability than oral dosing of cannabinoids. All blood samples for PK analysis will be separated by centrifugation immediately following the draw and plasma will be stored at -80° C until analysis. Samples will be analyzed using a literature method based on LC/MS technology.²⁰ The method will be translated and validated in the lab of [name], Director of the Penn State Cancer Institute emerging ADME/PK & Correlative Science Shared Resource using a Waters Acquity UPLC system with MS/MS multiple reaction monitoring of the CBD fragmentation m/z 313.10 to m/z 245.2 in negative ion mode. Quantification will be based on use of d3-CBD (Sigma Aldrich) as an internal standard.

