7.2.1 Prescreen

Patients will be screened and recruited as outlined in Section 4, Recruitment Methods. If they meet outlined criteria they will be contacted by the study coordinator for Study visit 1 - Screening Visit.

During prescreening, the subject will confirm whether she is currently taking hormonal medication for contraception and/or endometriosis related issues. Depending on her current medication, she may need to delay enrollment into the study. If they are not already on NETA, they will need to consult with their primary physician in order to initiate the medication. Patients will also be advised to consult with their primary physician in order to determine whether they can initiate NETA and stop their current medication regiment. Once the patient is enrolled in the study, NETA will be provided by the IDS.

If the patient is not currently on NETA, they will need to be transitioned as follows:

- 1. None No delay
- 2. Combined oral contraceptive No delay
- 3. Etonogestrel/ethinyl estradiol vaginal ring No delay
- 4. GnRH antagonist (e.g. Orlissa) No delay
- 5. Long acting reversible contraception (Progesterone IUD, Copper IUD) No delay
- 6. GnRH agonist (e.g. Lupron Depot): 3.75 mg must wait 1 month from administration of prior injection and 11.25 mg- must wait 3 months from administration of prior injection.
- 7. Injectable Progesterone (Depo Provera) Must wait 3 months from administration of prior injection
- 8. Progestin-containing contraceptive implant Excluded from the studied

For women using methods listed #1-4, they will stop/remove this form of contraception and be transitioned immediately to NETA.

For women using LARCS listed #5, they can continue this form of contraception and be transitioned immediately to NETA.

For women using methods #6-7, they must wait the listed time prior to initiation of NETA.

All subjects will be required to be on NETA for 30 days prior to the enrollment visit.

The NETA is intended for the purposes of endometriosis related standard of care and is not considered an appropriate contraceptive method for patients. Acceptable methods of contraception are listed in Section 7.2.3.

We will confirm they are not currently taking any of the exclusionary medications/drugs in their described manners. If they have recently stopped the below products, their required washout period is listed below:

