7.2.2 Study Visit 1: Screening Visit

Pre-screening will take place in the Penn State Hershey MIGS clinic or over the phone with women identified as potential candidates for study participation via prior clinic visits. If the subject meets all pre-screening criteria, she will return for a screening encounter and undergo informed consent prior to any study procedure. The subject will be given ample time to ask questions or voice concerns about the study.

A detailed history and physical exam will be performed, particularly to assess for concomitant use of anti-epileptic drugs and or underlying risk of liver dysfunction. We will need approximately 8-10 cc of blood (approximately 2 teaspoons).

- 1. Liver function tests (LFTs) will be drawn.
- 2. Baseline CBC and BMP will be drawn.
- 3. Screening urine toxicology will also be performed to confirm no recent THC use.
- 4. Urine pregnancy test will be collected.
- 5. Pain medication and narcotic usage from the prior month will be assessed.
- 6. Suicidal ideation will be assessed via the Columbia-Suicide Severity Rating Scale (C-SSRS).

If the subject is found to be pregnant, have evidence of underlying hematologic/ urologic/ hepatobiliary dysfunction or a positive urine toxicology for recent THC use, the subject will be excluded.

Current medication usage will be reviewed thoroughly with special attention paid to Cytochrome P450 (CYP) inducers and inhibitors as well as Substrates of uridine 5'-diphosphoglucuronosyltransferase (UGT). If the subject is screened into the study, their condition and corresponding medication will be recorded throughout the study. Please refer to Section 10 Risks, Drug Interactions, for additional guidelines.

Baseline survey data will be collected and entered into the RedCap secured database. This information will include the WERF EPHect Questionnaire.

At this time subjects will be set up for emails to complete VAS scores directly into RedCap. If not done already, the subject will be transitioned to norethindrone acetate to start taking immediately and given instruction on how to complete the VAS scores and study questions. It will be explained to the patient that she must complete 5 out of 7 days of surveys to be enrolled into the study. If the subject is unable to complete the 5 out of 7 days, the subject will be given one additional week to determine if compliance is attainable. If the subject is unable to do so, they will screen fail.

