7.2.3 Study Visit 2 – Enrollment Visit

The subject will be scheduled for a randomization/enrollment 1-2 weeks after the screening visit. The randomization will be double blind and 1:1:1. The patient will have been expected to be on norethindrone acetate (NETA) for 30 days prior to the enrollment visit. Dosing for norethindrone acetate will start at 5mg oral daily, but may be adjusted from 2.5 mg to 15 mg depending on the subject's needs to achieve amenorrhea as this standard treatment for endometriosis or to increase compliance by reducing side effects. The study team will be responsible for adjusting dosages at subsequent study visits 3 and 4. At this visit, the subject will be randomized into Group A, Group B, Group C by IDS as long as the subject has met all the criteria for enrollment. The groups are listed below:

Group	Treatment
А	Norethindrone acetate + Placebo (Hemp Seed Oil)
В	Norethindrone acetate + low dose CBD (10mg sublingual daily)
С	Norethindrone acetate + high dose CBD (20mg sublingual daily)

The subject will be given a 4 week supply of (1) placebo (2) low dose CBD or (3) high dose CBD product and instructed on its application. The subject will also receive a 4 week supply of norethindrone. Refer to the following:

- a. In the morning, take the norethindrone acetate orally with a sip of water at approximately the same time each day. This can be taken on an empty or full stomach.
- b. Prior to bed, you will administer the study drug.
 - 1. Please refrain from eating (drinking is permissible) 60 minutes prior to administration.
 - 2. Place 4 drops of the study drug under your tongue.
 - 3. Hold the study drug under the tongue for 60 seconds. After that time, swallow any remaining drug.
 - 4. Repeat steps 2 and 3 for a total of 8 drops.

Please avoid eating, drinking or smoking for 2 hours after administration.

A focus group was conducted to determine the optimal route of administration of the study drug. 1 application of 8 drops of the study drug versus 2 applications of 4 drops were compared and it was determined that the latter method was preferred.

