7.3 Duration of Participation

Study participation is expected to be 13-14 weeks. For those who participate in the optional PK study, participation may extend to 12-24 weeks post-enrollment.

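### No pregnancy test is scheduled at randomization, during the 8 dosing weeks, or before the optional PK dose

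*Combined protocol and SAP*

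**What the plan says.** The pregnancy-test row in the schedule of procedures (Section 7.2) carries two marks, and the visit text shows where they fall. Section 7.2.2 (Visit 1, screening) states "Urine pregnancy test will be collected". Section 7.2.6 (Visit 5, week 12, four weeks after treatment ends) adds final bloodwork "in addition to another urine toxicology and urine pregnancy test". Sections 7.2.3, 7.2.4 and 7.2.5 list other assessments for Visits 2, 3 and 4 but no pregnancy test, although study drug is dispensed at Visits 2 and 3.

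For the optional PK visit, where a further 20 mg of CBD is given, Section 7.2.7 relies on the screening already done: "we will not be repeating any additional testing on these patient". On timing it says "They will remain eligible to participate in this study for up to 3 months from the date of their last visit".

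The screening interval is given in Section 7.2.3: "The subject will be scheduled for a randomization/enrollment 1-2 weeks after the screening visit". Section 7.3 is consistent with that: "Study participation is expected to be 13-14 weeks".

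Pregnancy is an exclusion (Section 3.2), a ground for immediate withdrawal (Section 3.3.1) and a trigger for maternal, fetal and neonatal follow-up (Section 3.3.2). Section 10.0 requires women not to be pregnant at the start and acknowledges that human developmental data on CBD are inadequate.

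**The concern.** These rules work only if a pregnancy is recognized, yet no test is tied to first dispensing, resupply or the PK dose. Between the two scheduled tests, recognition depends on self-report, the menstrual diary and clinical suspicion.

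Three features of the plan weaken those routes.

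- Women on combined pills, vaginal rings or GnRH antagonists stop them and move to norethindrone acetate (NETA), which Section 7.2.1 itself says is not suitable as contraception. Barrier methods are then acceptable, and Section 7.2.3 concedes that no listed method is fully effective.
- NETA is adjusted toward amenorrhea (Section 7.2.3), so a missed period is a weaker signal.
- The assessment at Visits 2-5 names liver, vascular, migraine and visual symptoms, but neither pregnancy nor contraceptive use.

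The reasoning for the PK visit is the least secure. Earlier screening cannot settle a status that can change afterwards, and the text describes no diary entries after Visit 5. At stake is avoidable fetal exposure to CBD, not the validity of the efficacy comparison.

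**Working it through.** The plan gives no figure to reproduce here, so the check is calendar arithmetic followed by a rough bound on the number of women affected.

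**Inputs from the protocol.** Screening to randomization 1-2 weeks (7.2.3); dosing 8 weeks, resupply at week 4, Visit 5 at week 12 ± 3 days (7.2.4-7.2.6); PK window 12-24 weeks after enrollment, or 3 months from the last visit (7.2.7); 36 women randomized 1:1:1 (8.1, 7.2.3); at most 4 PK volunteers (7.1).

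**Timetable check.** 1-2 weeks + 12 weeks = 13-14 weeks, which matches Section 7.3.

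**Age of the latest scheduled result under the current plan**

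| Event | Calculation | Age |
|---|---|---|
| First dose | screening interval | 1-2 weeks |
| Resupply, Visit 3 | 4 + (1 to 2) | 5-6 weeks |
| Last dose | 8 + (1 to 2) | 9-10 weeks |
| PK dose, 24-week limit | 0 to (24 − 12) + 3/7 | 0-12.4 weeks |
| PK dose, 3-month wording | 0 to about 13 | 0-13 weeks |

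**A contingent case.** Section 7.2.1 says "All subjects will be required to be on NETA for 30 days prior to the enrollment visit", while Section 7.2.2 says that, if not done already, "the subject will be transitioned to norethindrone acetate to start taking immediately" at screening. If NETA does start at Visit 1, the gap to the first dose is at least 30/7 = 4.3 weeks, and to the last dose 8 + 4.3 = 12.3 weeks. This conflicts with the 1-2 week interval, so I give it no weight in the conclusion.

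**Expected conceptions.** The protocol gives no pregnancy rate. I assume 1-15% per year on permitted methods and count every woman as at risk, so these are upper bounds. Women on CBD: 36 × 2/3 = 24.

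- Last test to last dose: 24 × 9/52 = 4.15 to 24 × 10/52 = 4.62 woman-years. Low end 4.15 × 0.01 = 0.04; high end 4.62 × 0.15 = 0.69.
- Part a Visit 2 test could reach: 24 × 1/52 = 0.46 to 24 × 2/52 = 0.92 woman-years, so 0.005 to 0.14.
- Part a Visit 3 test could reach: 24 × 4/52 = 1.85 woman-years, so 0.02 to 0.28.
- Both together: 24 × 5/52 = 2.31 to 24 × 6/52 = 2.77 woman-years, so 0.02 to 0.42.
- PK group: 0 to 4 × 13/52 = 1.0 woman-year, so 0 to 0.15.

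**Effect of added tests on the schedule.** The longest untested run of dosing falls from 8 weeks to about 4. With ± 3 days at each visit, Visit 3 to Visit 4 spans 53 − 31 = 22 to 59 − 25 = 34 days. The age of the result at randomization and at the PK dose falls to 0 days.

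**Dose margin.** For an assumed weight of 50-90 kg, 20 mg/day is 20/50 = 0.40 to 20/90 = 0.22 mg/kg/day. Section 10.0 places the animal effects at 7-16 times 20 mg/kg/day. Read as dose multiples, that is 140/0.40 = 350 to 320/0.222 = 1,440 times the trial dose. If sublingual absorption were complete against the 6% oral figure in Section 2.3, the margin would be 350 × 0.06 = 21 to 1,440 × 0.06 = 86 times.

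**The case against.** The strongest reply is that the gap is small and already guarded. Contraception is mandatory, IUDs may continue, women trying to conceive are excluded, and the diary records menstrual pattern. A woman found pregnant at screening is excluded, and randomization requires that all entry criteria be met, so at Visit 2 only a repeat test after 1-2 weeks is missing. Testing on clinical suspicion is not barred. No rule in the protocol sets a testing frequency. The PK exposure is one 20 mg dose in at most four women, and the Visit 5 test precedes it.

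Much of this stands and keeps the point modest. Two parts need an explicit answer.

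- The 0.04-0.69 figure is not the benefit of the fix. Conceptions in the final 4 dosing weeks, 4/10 to 4/9 or 40-44% of the total, would not be caught by tests at Visits 2 and 3. A Visit 3 test also only shortens exposure that has already begun; among the main-trial tests, only the one at Visit 2 prevents exposure outright. The relevant figure is the smaller 0.02-0.42, still an upper bound on an assumed rate.
- Low dose argues for a low risk but does not remove the case for testing. Section 10.0 says the doses linked to raised transaminases were well above those planned here, yet liver tests are still repeated at weeks 4, 8 and 12.

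**Conclusion.** The concern holds. The schedule table and the visit text agree that no pregnancy test falls at randomization, during dosing or before the PK dose, and this part does not depend on any assumption. The size is modest: well under one expected conception on the assumed 1-15% yearly rate with all women counted as at risk. Exposure for the full 8 weeks would need conception before or near first dosing, failed contraception and no recognition at Visit 3. The clearest gaps are first dispensing and a late PK dose, because a test there prevents exposure altogether. Sample size and the primary analysis are unaffected. The change should be made because the potential harm is serious and the remedy is small; it does not call the design into question.

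**What to change.** Use the urine pregnancy test already in the protocol at three further points:

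1. Visit 2, before first dispensing. This also closes the gap however the NETA lead-in conflict is resolved.
2. Visit 3, before resupply.
3. The PK day, before the 20 mg dose, alongside the pre-dose salivary pH.

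Amend Section 7.2.7 to say that no testing is repeated except a urine pregnancy test before the PK dose, and update the schedule table. Test all arms so that the blind is kept, and exempt women who have had a hysterectomy. If a dispensing visit is held remotely, require a home test reported before drug is released. Visit 4 can be left out because no study drug is dispensed there.

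The cost is at most 36 + 36 + 4 = 76 tests, fewer with exemptions, at visits already planned and with no invasive procedure. Each woman has two extra urine tests, or three if she volunteers for the PK visit. Remote dispensing would need home kits and a simple release check. The protocol gives no unit price, so calling this cheap rests on the number of tests. Adding Visit 4 as well would bring the total to 36 × 3 + 4 = 112 and would only bring detection forward from week 12 to week 8, after dosing has ended.

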7.3 Duration of Participation

Study participation is expected to be 13-14 weeks. For those who participate in the optional PK study, participation may extend to 12-24 weeks post-enrollment.

7.4 Test Article(s) (Study Drug(s) and/or Study Device(s))

7.4.1 Description

Cannabis is a well-known plant that contains more than 500 identified phytochemicals of which over 100 are cannabinoids. The most widely studied is Δ^9 -tetrahydrocannabinol (Δ^9 -THC), which is the major psychoactive component of *Cannabis*, but Cannabidiol (CBD) has been increasingly favored for its reduced side effect profile and potential health benefits. CBD was first isolated

from *Cannabis* in the 1940s. CBD, unlike Δ^9 -THC, does not bind to CB1 and CB2 receptors, which accounts for its lack of typical psychotropic effects, but is still appears to work via alternative mechanisms via the endocannabinoid system. The ECS has been linked mood, immunocompetency, cell proliferation and inflammation.

The CBD used for the study will be purchased from an online retailer, Nuleaf Naturals. We will purchase their full spectrum hemp CBD oil (60mg/mL). Please refer to 7.4.6.1 in regards to internal and external validity testing for this product.

7.4.2 Treatment Regimen

Group	Treatment
А	Norethindrone acetate (5mg daily) + Placebo
В	Norethindrone acetate (5mg daily) + Low dose CBD (10mg sublingual daily)
С	Norethindrone acetate (5mg daily) + High dose CBD (20mg sublingual daily)

Arm A (Placebo): In Arm A, the participant will be placed on the daily placebo and standard endometriosis treatment (norethindrone acetate 5mg daily, initial dose) medication. Placebo will be taken sublingually and the norethindrone will be taken orally. Norethindrone will be taken for up to 12 weeks during the study period and the study drug for up to 8 weeks during the study period.

Arm B (Low Dose CBD): In Arm B, the participant will be placed on the daily low dose CBD (10mg sublingual daily) and standard endometriosis treatment (norethindrone acetate 5mg daily, initial dose) medication. CBD will be taken sublingually and the norethindrone will be taken orally. Norethindrone will be taken for up to 12 weeks during the study period and the study drug for up to 8 weeks during the study period.

Arm C (High Dose CBD): In Arm C, the participant will be placed on the daily high dose CBD (20mg sublingual daily) and standard endometriosis treatment (norethindrone acetate 5mg daily, initial dose) medication. CBD will be taken sublingually and the norethindrone will be taken orally. Norethindrone will be taken for up to 12 weeks during the study period and the study drug for up to 8 weeks during the study period.

The subject randomized in a double-blinded fashion to a 4 week supply of either the (1) placebo (2) low dose CBD or (3) high dose CBD product and instructed on its application. The subject will also receive a 4 week supply of norethindrone, which will be unblinded. Refer to the following:

- c. In the morning, take the norethindrone acetate orally with a sip of water at approximately the same time each day. This can be taken on an empty or full stomach.
- d. Prior to bed, you will administer the study drug.
 - 1. Please refrain from eating (drinking is permissible) 60 minutes prior to administration.
 - 2. Place 4 drops of the study drug under your tongue.
 - 3. Hold the study drug under the tongue for 60 seconds. After that time, swallow any remaining drug.
 - 4. Repeat steps 2 and 3 for a total of 8 drops.

Please avoid eating, drinking or smoking for 2 hours after administration.

Patient instructions will be identical. The placebo dose will be 8 drops of oil (8 drops of hemp seed oil - Omg of CBD), the low dose CBD group will receive 8 drops of oil (8 drops of a solution of 60mg/mL CBD oil + hemp seed oil in a 1:1 ratio for a dose of 10mg of CBD), while the high Page 23 of 37 (V.01/21/2019)

dose CBD group will receive 8 drops of oil (8 drops of 60mg/ml CBD oil for a dose of 20mg of CBD).

The dosage and route of administration of CBD is highly varied. In regards to dosage, human studies have been performed using CBD dosages that range from 1.5mg – 800mg per day.¹⁸ These studies have consistently shown that high doses of oral CBD fail to produce the typical adverse effects (impaired psychomotor & cognitive function) seen with Δ^9 -THC and that CBD is generally well tolerated with a reasonable safety profile.¹⁰

In regards to the route of administration, multiple methods have been reported that include oral, sublingual, intranasal, intravenous and inhalation via smoking. CBD is known to undergo extensive first pass effect (bioavailability of 6%) making oral administration ineffective in delivery. On the other hand, sublingual administration, which will bypass this effect, resulted in consistent mean CBD concentrations compared to oromucosal spray or oropharygyneal administration. Moreover, this route is preferable to inhalation given its ease of use.¹⁸

Of note the mean half-life of CBD is reported as 1.09 and 1.97 hours (10mg vs 20mg) after single oral administration, but after chronic oral administration the mean half-life was noted to be 2-5days.¹⁸

With current data, we believe 10mg vs. 20mg of CBD given sublingually over 8 weeks to be an appropriate dose to see effect in our primary outcome without any overt or serious risk to our participants. We do not foresee dose adjustments to these medications.

